# Display probabilities and p-value of pairwise contrast
qflextable(emm.ord) %>%
set caption(paste0("Probabilities for the Hoehn & Yahr stage at 52 weeks in
the treatment groups (", p format(comp$p.value, digits = 3, add.p =
T),")"))
```

#### **Exploratory analyses**

The change from baseline to week 52 in the NAD metabolome, serum NfL levels, and NAD/ATP-  $\alpha$  ratio, will be compared between the treatment groups by MMRM, following the same lines as the primary outcome. Least square mean changes for both groups as well as the difference between the least squares treatment group means will be reported with 95% CIs and p-value testing the null hypothesis of no treatment effect.

Furthermore, the primary endpoint will be analyzed using the per-protocol set as defined in Section 3.3. If the selection between the treatment arms is skewed, a propensity score based method will be applied to adjust for potential confounding.

Confidential Page 16 of 21

### 5.3 Missing data

While the MMRM model described above is robust to a certain extent to missing data (in particular when missing at random (MAR)), a sensitivity analysis using multiple imputation will be conducted to assess the robustness of the results. For this purpose, reference based multiple imputation will be performed using the R package *rbmi* (without MAR assumption).

#### 5.4 Additional analyses

#### Sensitivity analysis of the primary analysis

To assess the robustness of the primary analysis, sensitivity analysis will be performed by using multiple imputation as described in the previous section.

In addition, the change in Levodopa dose (part of the standard-of-care PD regimen) and the time elapsed from levodopa intake until performance of the visit will be compared between the groups. If there are differences between the groups, we will model the hypothetical effect if the levodopa dose was constant and could not be changed.

In addition, the presence of dyskinesia during examination (from the MDS-UPDRS III scale) will be compared between the groups. If there are differences between the groups, we will model the hypothetical effect if dyskinesia was not present during the examination.

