# 1.2 Objectives and Endpoints

The NOPARK study investigates the hypothesis that oral administration of NR can ameliorate neuronal metabolism, increase neuronal resilience, and inhibit neurodegeneration, resulting in amelioration of clinical symptoms and delayed PD progression. Primary and secondary endpoints are listed in Table 1.

Table 1 Objectives and related endpoints

	Objective	Endpoint
Primary	To compare the effectiveness of orally administered nicotinamide riboside (NR) 500 mg twice per day versus placebo on delaying disease progression in PD.	Change from baseline in MDS-UPDRS Total Score (sum of parts I, II and III) in the ON-medication state at week 52.
Key secondary	To compare the effectiveness of orally administered nicotinamide riboside (NR) 500 mg twice per day versus placebo on delaying the progression of motor symptoms in PD.	Change from baseline in the MDS- UPDRS Part III in the ON-medication state at Week 52.
	To compare the effectiveness of orally administered nicotinamide riboside (NR) 500 mg twice per day versus placebo on delaying the progression of dopaminergic nigrostriatal denervation in PD.	Change from baseline in the mean striatal binding ratio (SBR) of the putamen, bilaterally, as measured [1231]FP-CIT Single-Photon Emission Computed Tomography (SPECT) Imaging of the Dopamine Transporter (DaT, DaTscan) at Week 52.
	To compare the effectiveness of orally administered nicotinamide riboside (NR) 500 mg twice per day versus placebo on delaying the progression	Change from baseline in the MDS-UPDRS Part I in the ON-medication state at Week 52.

Confidential Page 6 of 21

	Objective	Endpoint
	of non-motor symptoms in daily living in PD.	
	To compare the effectiveness of orally administered nicotinamide riboside (NR) 500 mg twice per day versus placebo on delaying the progression of motor aspects of experiences of daily living in PD.	Change from baseline in the MDS- UPDRS Part II in the ON-medication state at Week 52.
	To compare the effect of orally administered nicotinamide riboside (NR) 500 mg twice per day versus placebo on the progression of nonmotor symptoms in PD.	Change from baseline in the NMSS Score in the ON-medication state at Week 52.
Other secondary	To compare the effect of orally administered nicotinamide riboside (NR) 500 mg twice per day versus placebo on the progression of cognitive dysfunction in PD.	Change from baseline in the MoCA score in the ON-medication state at Week 52.

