### 2.3 Sample Size

For sample size calculation we assume a common standard deviation of 16 points in the total MDS-UPDRS (parts I, II and III) and an overall type 1 error rate of 5%. Such a standard deviation was seen in Holden et al (2018). This estimate is further supported by a blinded sample size review performed on a blinded data export from August 23, 2024. A sample size of 162 participants per group gives an 80% power given a difference of 5 points in the total MDS-UPDRS at 52 weeks between the NR and the placebo group (324 in total). A difference of this magnitude was reported to be within the clinically meaningful range (see Wyman-Chick et al (2018)). Accounting for approx. 20% drop out, 200 participants per group (400 in total) are required.

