#### 3.3 Analysis populations

The primary analysis will follow the intention-to-treat (ITT) principle. The **ITT population** contains all randomized patients with at least two post-baseline measurements, regardless of protocol adherence.

The **safety population** contains all enrolled patients with treatment as actually received.

In a secondary **per-protocol analysis set**, participants are excluded if any of the following apply:

- Failure to meet eligibility criteria
- Incorrect randomization
- Missing primary outcome at any visit
- Treatment compliance < 90%

- Change in standard-of-care PD regimen during the trial

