#### Subgroup analysis

Subgroups analyses are planned to be performed for:

- Age (median split; i.e. ≤ median vs > median)
- Hoehn & Yahr (Score ≤ 1 vs >1)
- Sex (Male/Female)
- Disease duration (Time from anamnestic onset of PD to randomization; dichotomized by median split)
- Motor phenotype (Postural Instability and Gait Difficulty [PIGD] vs non-PIGD)
- Dopaminergic therapy dose (3 groups: 300, 450, 600 mg levodopa).

The described MMRM for the primary endpoint will be extended to include the respective baseline factor and its interaction with treatment. Results will be graphically summarized in a forest plot.

For continuous variables such as age and disease duration the interaction with the treatment effect will be modeled using flexible splines. The treatment effects with confidence intervals will be plotted against the baseline variable.

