#### **Major Protocol Deviations**

- 1. Enrolment of a participant not meeting inclusion/exclusion criteria (e.g., PD diagnosis >2 years, H&Y ≥3, no DAT confirmation, use of high-dose vitamin B3).
- 2. Informed consent not obtained prior to study procedures.
- 3. Incorrect randomization or failure to randomize per protocol.
- 4. Non-adherence to investigational product (IP) administration with < 90% compliance or not taking study medication for > 14 days consecutively, or not taking study medication within 3 days from the last visit.
- 5. Non-adherence to the standardized dopaminergic regimen (Regimens A–C, see study protocol) after baseline.
- 6. Missing primary efficacy endpoint assessment (MDS-UPDRS Total) at any visit.

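### The constant-therapy sensitivity analysis in SAP 5.4 tracks levodopa dose only, so changes in other dopaminergic drugs are handled only by exclusion in the exploratory per-protocol analysis

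*SAP*

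**What the plan says.** Table 1 (section 1.2) defines the primary endpoint as "Change from baseline in MDS-UPDRS Total Score (sum of parts I, II and III) in the ON-medication state at week 52". Section 3.3 keeps patients in the primary analysis whether or not they adhered to the protocol.

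Section 5.4 addresses symptomatic treatment in a sensitivity analysis. Two quantities are compared between the groups: "the change in Levodopa dose (part of the standard-of-care PD regimen"), and the time between levodopa intake and the visit. If the groups differ, "we will model the hypothetical effect if the levodopa dose was constant and could not be changed". No other dopaminergic drug is named there, and no total-dose or levodopa-equivalent measure appears anywhere in the SAP.

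Elsewhere the SAP uses the whole regimen:

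- Section 3.3 removes a patient from the per-protocol set for "Change in standard-of-care PD regimen during the trial".
- The appendix lists as a major deviation "Non-adherence to the standardized dopaminergic regimen (Regimens A–C, see study protocol) after baseline". Its table keeps such patients in the full analysis set, drops them from the per-protocol set, and gives confounding of the efficacy results as the reason.
- Section 5.2 (exploratory analyses) states that "the primary endpoint will be analyzed using the per-protocol set as defined in Section 3.3", with a propensity-score method if the arms turn out to be selected unevenly.

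**The concern.** In a progressive disease followed for 52 weeks, some patients will have symptomatic therapy increased, and an ON-state score then understates how far they have progressed. Section 5.4 asks the right question: what would the effect have been had therapy not changed? But it measures therapy by one component.

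A patient whose levodopa is unchanged while another dopaminergic drug is started or raised counts as unchanged. If such changes are more frequent in one arm, the constant-levodopa estimate keeps that imbalance while appearing to have dealt with symptomatic treatment. With an excess on placebo it leans towards no effect; with an excess on NR it leans the other way. What is at stake is how far this sensitivity analysis can be relied on when the primary result is interpreted.

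**Working it through.** **1. What each analysis registers.** This assumes that other dopaminergic drugs count as part of the standard-of-care regimen, as the wording of 5.4 implies.

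| Change after baseline | Levodopa change (5.4) | Total dopaminergic change | Per-protocol set (3.3) |
|---|---|---|---|
| None | 0 | 0 | kept, if no other reason applies |
| Levodopa raised, others unchanged | + | + | excluded |
| Levodopa unchanged, another drug added or raised | 0 | + | excluded |
| Levodopa lowered, another drug added | − | 0, + or −, depending on doses | excluded |

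The two measures agree in the first two rows. In the third, 5.4 sees nothing. In the fourth it sees a reduction that may not be one in total, so an adjustment could go in the wrong direction.

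**2. What triggers the model.** It is run if the groups differ in levodopa change or in time since intake. An imbalance confined to other drugs starts nothing.

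**3. What the per-protocol analysis estimates.** It does remove the patients in rows 3 and 4. But it selects on an event after randomisation that may itself reflect progression. It also drops patients for other reasons, such as compliance below 90% or a missing primary outcome at any visit, and it uses propensity adjustment only conditionally. It compares patients whose therapy happened to stay the same. It does not estimate the effect under constant therapy in all randomised patients.

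**4. Yardstick from the SAP (section 2.3).** Inputs: SD 16, difference 5, two-sided 5%, power 80%.

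- n per group = 2 × (1.960 + 0.842)² × 16² / 5² = 160.7, so 161. The t-test version gives 161.7, so 162, as stated. Power at 162 per group is 0.803.
- Standard error of a simple difference: 16 × √(2/162) = 1.78 points.

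**5. Illustrative size.** The SAP gives no rates, so these shares and effects are assumptions. Residual bias in the constant-levodopa estimate = (share on placebo − share on NR with a non-levodopa increase) × reduction in ON score per such patient.

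| Placebo vs NR | Reduction per patient | Residual bias | Share of 5 points | In standard errors |
|---|---|---|---|---|
| 10% vs 5% | 4 points | 0.05 × 4 = 0.2 | 4% | about 0.1 |
| 15% vs 5% | 5 points | 0.10 × 5 = 0.5 | 10% | about 0.3 |
| 20% vs 5% | 8 points | 0.15 × 8 = 1.2 | 24% | about 0.7 |

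If the shares are equal in the arms, or such changes do not occur, the bias is zero.

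**The case against.** The strongest reply is that levodopa may be nearly all that can vary. Treatment follows standardised Regimens A–C, and the subgroup in 5.4 is given as "Dopaminergic therapy dose (3 groups: 300, 450, 600 mg levodopa"). Three regimens beside three levodopa doses is consistent with levodopa being what distinguishes them and anything else being fixed. That is possible, but the SAP does not define the regimens. The subgroup concerns a baseline factor, whereas the deviation plan expects departures after baseline and does not limit them to levodopa. The reply bears on how large the gap is. It does not show that there is none.

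A reader might infer that progression treated with other drugs goes wholly uncorrected. The SAP does not support that. Such patients leave the per-protocol set, the primary endpoint is re-analysed there, and the appendix has deviations summarised by arm, so an imbalance in regimen departures should be visible. The remedy is weak for the reasons given, but it exists.

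A reader might also see a contradiction between 3.3 and 5.4. They are different analyses with different purposes, and nothing obliges them to share a variable. The point is that 5.4 uses a narrower measure than the confounder the SAP itself identifies.

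It is also fair to say that the imaging endpoint, change in striatal binding ratio, is not an ON-state score, so a null clinical result would not be left without other evidence.

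**Conclusion.** The point holds as a limited defect in a sensitivity analysis. Section 5.4 is triggered by and adjusts for levodopa alone, while the rest of the SAP treats the whole dopaminergic regimen as capable of distorting efficacy. Changes in other dopaminergic drugs are met only by exclusion in an exploratory analysis.

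The size is unknown. The range of 0.2 to 1.2 points rests entirely on assumed rates and effects, and two of the three cases lie below about 0.3 of a standard error.

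It would be tempting to turn such dilution into lost power for the trial: a 10% excess with 5 points each leaves 5 − 0.5 = 4.5 points and power 0.716 instead of 0.803. That reading should not be adopted here. Any such loss comes from scoring in the ON state regardless of therapy changes, and it would be the same whichever variable 5.4 used. The primary ITT model and its test are unaffected.

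The change is still worth making before unblinding, because it is cheap and gives the same answer as the present plan if other drugs never change.

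**What to change.** In section 5.4, define both the between-group comparison and the hypothetical scenario on total dopaminergic therapy: levodopa-equivalent daily dose of all dopaminergic drugs, derived at baseline and Weeks 13, 26, 39 and 52 from the concomitant-medication records listed in Table 3. State the scenario as no change in total dopaminergic therapy since baseline. Fix the conversion table before unblinding, and keep the levodopa-only version as a supplement. If Regimens A–C rule out changes in other dopaminergic drugs except as deviations, say so in 5.4.

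The cost is SAP wording and one derived variable, with no new visits or assessments. There are two limits. The conversion is approximate, although leaving the other drugs out sets their contribution to zero. And Table 3 lists concomitant medication without saying that doses are recorded, so their availability must be checked first; if they are missing, a yes/no indicator per visit for another dopaminergic drug started or raised would be a coarser substitute. The change concerns analysis only and alters no treatment rule.

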#### Subgroup analysis

Subgroups analyses are planned to be performed for:

- Age (median split; i.e. ≤ median vs > median)
- Hoehn & Yahr (Score ≤ 1 vs >1)
- Sex (Male/Female)
- Disease duration (Time from anamnestic onset of PD to randomization; dichotomized by median split)
- Motor phenotype (Postural Instability and Gait Difficulty [PIGD] vs non-PIGD)
- Dopaminergic therapy dose (3 groups: 300, 450, 600 mg levodopa).

The described MMRM for the primary endpoint will be extended to include the respective baseline factor and its interaction with treatment. Results will be graphically summarized in a forest plot.

For continuous variables such as age and disease duration the interaction with the treatment effect will be modeled using flexible splines. The treatment effects with confidence intervals will be plotted against the baseline variable.

#### 5.5 Harms

Safety endpoints will be analyzed descriptively by treatment group using standard statistic measures depending on the data type (e.g. frequencies and percentages for categorical variables and mean, standard deviation, median and IQR for continuous variables). For events of particular interest (e.g. neoplastic disease and cardiovascular events) Kaplan-Meier curves or cumulative incidence functions in case of competing events stratified by treatment group will be computed and compared by log-rank tests resp. Gray's test. For recurrent events and to account for variable

Confidential Page 17 of 21

follow-up times, event rates will be reported with rate ratios comparing NR with placebo and 95% CI. We will use Poisson regression with adjustment for over dispersion or negative binomial regression models with offset for follow-up time and possibly a mixture component to account for zero-inflation.

```
library(gtsummary)
library(survival)
library(ggsurvfit)
library(tidycmprsk)
library (MASS)

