	To compare the effect of orally administered nicotinamide riboside (NR) 500 mg twice per day versus placebo on quality of life in PD.	Change from baseline in the EQ-5D-5L index value, at week 52.
	To compare the effect of orally administered nicotinamide riboside (NR) 500 mg twice per day versus placebo on the progression of Hoehn and Yahr stage.	Hoehn and Yahr stage at Week 52.
Exploratory	To compare the effect of orally administered nicotinamide riboside (NR) 500 mg twice per day versus placebo on brain NAD levels in PD.	Change from baseline in brain NAD/ATP-α ratio measured by 31 Phosphorus magnetic resonance spectroscopy (31P-MRS) in the posterior brain (encompassing the occipital, parietooccipital and posterior parts of the temporal cortex), at 52 weeks between participants according to treatment allocation.
	To compare the effect of orally administered nicotinamide riboside (NR) 500 mg twice per day versus placebo on systemic NAD metabolism	Comparison of the change from baseline in the NAD metabolome in whole blood, measured by liquid chromatography mass spectrometry (LC-MS), at 52 weeks between participants according to treatment allocation.
	To compare the effect of orally administered nicotinamide riboside (NR) 500 mg twice per day versus placebo on neuronal damage	Comparison of the change from baseline in serum neurofilament light-chain (NfL) levels, measured by Simoa analysis, at 52 weeks between participants according to treatment allocation.
Safety	To determine whether NR is safe and well tolerated.	Report of all Adverse Events (AE) of moderate or severe intensity and Serious Adverse Events (SAE).

Confidential Page 7 of 21

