# Kaplan-Meier curves with log-rank tests
SurvObj <- Surv(event time, event_status,</pre>
                                                   data
                                                          =
                                                                dataEndpoints)
km.by.treat <- survfit(SurvObj ~ group, data = dataEndpoints,</pre>
                        conf.type = "log-log")
plot(km.by.treat)
dataEndpoints %>%
  gtsummary::tbl survfit(y = Surv(time, status),
                          label header = "**{time} weeks**",
                          include = "group", times = 364/7) %>%
  gtsummary::add p()

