# Cumulative incidence functions with Gray's test
cuminc(Surv(event time, event status) ~ group, data = dataEndpoints) %>%
  ggcuminc() +
  ylim(c(0, 1)) + labs(x = "Days") +
  add confidence interval() +
  add risktable()
cuminc(Surv(event_time, event_status) ~ group, data = dataEndpoints) %>%
  tbl_cuminc(times = 364/7, label_header = "**{times} weeks cuminc**") %>%
  tidycmprsk::add_p()

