# Negative binomial Regression for recurrent events
mod.les <- glm.nb(event rate ~ intervention + center +</pre>
                   offset(log(FUtime)), data = secEndpoints)
tmt.means <- emmeans(mod.les, ~ intervention, type = "response",</pre>
```

Confidential Page 18 of 21

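### Time-to-first-event analyses of the events of particular interest have a test but no between-arm estimate with a confidence interval, and the planned rate ratio does not clearly cover them

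*SAP*

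**What the plan says.** The safety objective in Table 1 of SAP Section 1.2 is "To determine whether NR is safe and well tolerated". Section 5.5 opens with descriptive summaries by arm (frequencies and percentages, means, medians). It then selects some harms for more: "For events of particular interest (e.g. neoplastic disease and cardiovascular events) Kaplan-Meier curves or cumulative incidence functions", the latter where there are competing events, stratified by treatment group and "compared by log-rank tests resp. Gray's test".

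The next sentence begins "For recurrent events and to account for variable" follow-up times, and promises that "event rates will be reported with rate ratios comparing NR with placebo and 95% CI". These ratios come from Poisson or negative binomial models with an offset for follow-up.

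The code in Section 5.5 follows the same division:

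- The block headed "Kaplan-Meier curves with log-rank tests" fits curves by arm, tabulates the 52-week estimate by arm and adds a p-value.
- The cumulative incidence block plots curves by arm with a confidence band and risk table, tabulates 52-week values by arm and ends with a call to "tidycmprsk::add_p".
- The block that yields a between-arm ratio is headed "Negative binomial Regression for recurrent events".

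Section 3.1 sets a two-sided 5% level for all tests unless specified otherwise. Section 5.2 gives the safety analyses exploratory status without multiplicity adjustment.

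**The concern.** The harms that the SAP itself picks out are compared between arms by a test that returns no effect size. A confidence band around each arm's curve is not an interval for the difference between arms. Elsewhere the SAP does better: Section 5.2 asks for a between-group difference with 95% CI for the primary endpoint, the continuous secondary endpoints and the exploratory biomarkers.

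At stake is how well the safety objective can be answered. The trial is sized for MDS-UPDRS and follows patients for 52 weeks. If the selected events are few, a test result cannot show which sizes of harm the data rule out. An interval for the between-arm difference can.

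**Working it through.** **The plan's own calculation.** Section 2.3 is the only design calculation, and it concerns MDS-UPDRS. With a difference of 5, an SD of 16, two-sided 5% and 80% power:

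n per arm = 2 × (1.96 + 0.8416)² × 16² / 5² = 160.8, so 161.

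The SAP states 162, and a noncentral t calculation gives 80.1% power at 162, so the figure is reproduced. Allowing for 20% dropout, 162 / 0.80 = 203, against a stated 200 for approximately 20%. No calculation is given for safety events.

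**Inputs for this point.** From the SAP: 200 per arm, 1:1 allocation, 52 weeks, two-sided 5%. Assumed, because the SAP gives no incidence: 2% on placebo against 4% on NR (4 + 8 = 12 events), and 4% against 8% (8 + 16 = 24 events). A wider range of event totals is shown alongside. Early dropout is ignored.

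**Power of the log-rank test** (Schoenfeld, 1:1): power = Φ(½ × √d × ln HR − 1.96), where d is the total number of events.

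- HR 2, d = 12: ½ × 3.464 × 0.693 − 1.96 = −0.76, power 22%.
- HR 2, d = 24: ½ × 4.899 × 0.693 − 1.96 = −0.26, power 40%.

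| Total events | Power, HR 2 | Power, HR 3 | Approx. 95% CI around an observed HR of 1 |
|---|---|---|---|
| 6 | 13% | 27% | 0.20 to 4.95 |
| 10 | 19% | 41% | 0.29 to 3.45 |
| 20 | 34% | 69% | 0.42 to 2.40 |
| 30 | 47% | 85% | 0.49 to 2.05 |

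The last column is exp(±1.96 × 2/√d). For 80% power at HR 2, the events needed are 4 × (1.96 + 0.8416)² / (ln 2)² = 65.3, so 66 (71 by Freedman's formula). That is 66/400 = 16.5% of all patients.

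**What an interval would add.** Large-sample ratio CI: exp(ln(a/b) ± 1.96 × √(1/a + 1/b)), with a events on NR and b on placebo and equal exposure.

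- 4 v 4: ratio 1.0, CI exp(±1.96 × 0.707) = 0.25 to 4.0.
- 8 v 4: ratio 2.0, CI 2 × exp(±1.96 × 0.612) = 0.60 to 6.64. The exact conditional-binomial interval is 0.54 to 9.1, so the large-sample form is too narrow at these counts. The approximate log-rank p is 0.25.
- 8 v 4 as a risk difference: 4% − 2% = 2 percentage points. SE = √(0.04 × 0.96/200 + 0.02 × 0.98/200) = 0.0170, giving a simple Wald interval of −1.3 to 5.3 points.

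The 8 v 4 split is non-significant, yet its interval includes a doubling and much larger ratios. The p-value alone does not show this.

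**Does the rate ratio close the gap?** Its introductory words give two purposes: recurrent events and variable follow-up. Repeated cardiovascular events fall under the first. A broad reading of the second could take in any event. The code heading names recurrent events only, and a first neoplasm analysed as time to event is not a recurrent event. The scope is therefore left open for first events.

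**The case against.** The strongest reply is that the plan gives more than a p-value. Section 5.5 includes counts and percentages by arm, 52-week estimates by arm, a log-log interval type for the Kaplan-Meier fit and a confidence band on the cumulative incidence plot. Sparse events would be visible, and a reader could subtract the two 52-week estimates. The rate ratio with 95% CI may already cover cardiovascular events counted as recurrent. Safety analyses are labelled exploratory, and low power reflects the trial's size whatever the analysis. All of this stands. It limits the point to the time-to-first-event analyses and to a matter of reporting. It does not supply an interval for the between-arm difference, and exploratory status favours estimation over testing.

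Two stronger readings are tempting and not supported. A reader might infer that the SAP offers no between-arm estimate for any harm; the rate ratio shows otherwise. A reader might also infer that a non-significant test is meant to count as evidence of safety; the SAP says this nowhere.

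It is also fair to object that the event counts are assumed, and that a hazard ratio breaks down when one arm has no events. The first is why a range is shown. The second bears on the choice of measure, and the fix allows for it.

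**Conclusion.** The point holds in a limited form. For first events of particular interest, the between-arm comparison named in Section 5.5 and its code is a log-rank or Gray's test with no attached estimate and CI, and it is unclear whether the planned rate ratio extends to them. With 12 to 24 events in total, power for a doubling is about 22% to 40%; at 6 to 30 events it is 13% to 47%. These figures rest on assumed event counts, proportional hazards, 1:1 allocation and complete follow-up of 200 per arm. If the events proved common (about 66 or more in total), the test would be informative for a doubling, though an estimate would still be the more useful result.

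No primary or confirmatory conclusion changes. This is a low-cost improvement that helps the trial answer its own safety objective.

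**What to change.** In Section 5.5, for each event of particular interest, do one of the following:

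- Report the 52-week risk difference between arms with its 95% CI, using a method suited to sparse counts in place of the simple Wald form, and/or a hazard ratio with 95% CI where both arms have events (cause-specific under competing events).
- State that the planned rate ratio with 95% CI also covers first events, and change the heading of that code block to match.

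In either case, name the estimate as the main result and the log-rank or Gray's p-value as supportive. A cause-specific hazard ratio and Gray's test address different quantities and can disagree. The difference in cumulative incidence sits more naturally beside Gray's test.

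The cost is a sentence of text and a few lines of code, using data and packages already in the plan. The drawbacks are that the intervals will be wide and that a hazard ratio is not finite if one arm has no events, which favours the risk difference as the default.
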